5.1.4 Instructions Common to Investigational Study Treatments

5.1.4.1 Clinical Trial Material Specifics and Management Common to the Investigational Study Treatments

Investigational study treatment medication labels comply with the legal requirements of the United States and will be printed in the languages required in the countries in which the study is conducted.

Only qualified personnel who are familiar with procedures that minimize undue exposure to them and to the environment should undertake the preparation, handling, and safe disposal of chemotherapeutic agents.

Investigational study treatment clinical trial material should be stored in an area that is secure, with limited access and monitored for temperature using a calibrated thermostat.

Study site personnel will dispense investigational study treatment tablets or capsules on Day 1 of each dose cycle for the first 12 cycles on study, and then may reduce the frequency to every 2 cycles, at the discretion of the Investigator. Sufficient supply will be provided for each cycle and extra tablets/capsules may be provided to cover an additional 2 days in case of delayed clinic visits or lost tablets/capsules. Study tablets/capsules will be dispensed in HDPE bottles provided by the Sponsor.

All investigational study treatment supplies will be accounted for in the drug accountability inventory forms supplied by the Sponsor or using locally approved forms that include all required information. The drug accountability inventory forms must identify the study drug, including batch or lot numbers and account for its disposition on a patient-by-patient basis, including specific dates and quantities. The forms must be signed by the individual who dispensed the drug.

Patients will be asked to record their daily dosing on Sponsor provided diary cards and report any missed doses or lost doses at the next clinic visit. On the back of each Sponsor provided diary card, written dosing instructions for the specified investigational study treatment tablets or capsules are provided (e.g., fasting instructions, take with water, etc.). Patients should be told to bring study treatment bottle(s) (empty or not) and completed dosing diaries with them to the clinic visit for a compliance check and tablet/capsule count. Study site personnel will retain the bottle(s) until a monitor has completed reconciliation and retain dosing diaries with site study files.

At the end of the study, all unused investigational study treatment drug supplies must be destroyed in accordance with local Standard Operating Procedure provided to the Sponsor for the Trial Master File, or returned to the Sponsor or its appointed agent, as directed by the Sponsor.

5.1.4.2 Adverse Event Management Guidelines Common to the Investigational Study Treatments

Guidance on size of dose reduction steps in response to investigational study treatment toxicity are specified for glesatinib, sitravatinib and mocetinostat in Sections 5.1.1.3, 5.1.2.3 and 5.1.3.3, respectively.

Adverse event management guidance specific to investigational study treatments for glesatinib, sitravatinib and mocetinostat in Sections 5.1.1.4, 5.1.2.4 and 5.1.3.4, respectively.

5.1.4.2.1 Investigational Study Treatment Management in Event of Immune-Related Adverse Events

None of the three investigational study treatments has been associated with immune-mediated AEs. However, the potential exists for one or more of the treatments to contribute to immune-mediated AEs associated with nivolumab treatment. In the event of an immune-related AE during study treatment, administration of the investigational study treatment and nivolumab should be interrupted until the event stabilizes to Grade ≤1 (consistent with guidance provided in the OPDIVO US Prescribing Information replicated in Section 5.2.5). At the time of resumption of investigational study treatment dosing, a dose reduction may be implemented at the discretion of the Investigator.

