5.2.5 Nivolumab Adverse Event Management Guidelines

Table 17 reproduces AE management guidelines provided in OPDIVO US Prescribing Information, Section 5.

Table 17: Management of Nivolumab Immune-Related Adverse Events – Reprinted from OPDIVO US Prescribing Information

Immune-mediated AE Defined as Requiring Use of Corticosteroids and no Clear Alternate Etiology		
Immune-mediated pneumonitis	Monitor patients for signs with radiographic imaging and symptoms of pneumonitis. Administer corticosteroids at a dose of 1 to 2 mg/kg/day prednisone equivalents for moderate (Grade 2) or more severe pneumonitis, followed by corticosteroid taper. Permanently discontinue nivolumab for severe (Grade 3) or life-threatening (Grade 4) pneumonitis and withhold nivolumab until resolution for moderate (Grade 2) pneumonitis.	
Immune-mediated colitis	Administer corticosteroids at a dose of 1 to 2 mg/kg/day prednisone equivalents followed by corticosteroid taper for severe (Grade 3) or life-threatening (Grade 4) colitis. Administer corticosteroids at a dose of 0.5 to 1 mg/kg/day prednisone equivalents followed by corticosteroid taper for moderate (Grade 2) colitis of more than 5 days duration; if worsening or no improvement occurs despite initiation of corticosteroids, increase dose to 1 to 2 mg/kg/day prednisone equivalents. Withhold OPDIVO for moderate or severe (Grade 2 or 3) colitis. Permanently discontinue OPDIVO for life-threatening (Grade 4) or for recurrent colitis upon restarting OPDIVO.	
Immune-mediated hepatitis	Administer corticosteroids at a dose of 1 to 2 mg/kg/day prednisone equivalents for severe (Grade 3) or life-threatening (Grade 4) transaminase elevations, with or without concomitant elevation in total bilirubin. Administer corticosteroids at a dose of 0.5 to 1 mg/kg/day prednisone equivalents for moderate (Grade 2) transaminase elevations. Withhold OPDIVO for moderate (Grade 2) and permanently discontinue OPDIVO for severe (Grade 3) or life-threatening (Grade 4) immune-mediated hepatitis.	
Immune-mediated endocrinopathies		
Hypophysitis	Administer hormone replacement as clinically indicated and corticosteroids at a dose of 1 mg/kg/day prednisone equivalents followed by corticosteroid taper for moderate (Grade 2) or greater hypophysitis. Withhold OPDIVO for moderate (Grade 2) or severe (Grade 3). Permanently discontinue OPDIVO for lifethreatening (Grade 4) hypophysitis.	

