Table 17: Management of Nivolumab Immune-Related Adverse Events – Reprinted from OPDIVO US Prescribing Information (Continued)

Immune-mediated endocrinopathies (continued)		
Adrenal Insufficiency	Administer corticosteroids at a dose of 1 to 2 mg/kg/day prednisone equivalents followed by a corticosteroid taper for severe (Grade 3) or life-threatening (Grade 4) adrenal insufficiency. Withhold OPDIVO for moderate (Grade 2) and permanently discontinue OPDIVO for severe (Grade 3) or life-threatening (Grade 4) adrenal insufficiency.	
Hypothyroidism and Hyperthyroidism	Administer hormone-replacement therapy for hypothyroidism. Initiate medical management for control of hyperthyroidism. There are no recommended dose adjustments of OPDIVO for hypothyroidism or hyperthyroidism.	
Type 1 Diabetes Mellitus	Withhold OPDIVO in cases of severe (Grade 3) hyperglycemia until metabolic control is achieved. Permanently discontinue OPDIVO for life-threatening (Grade 4) hyperglycemia.	
Other Immune-med	liated AEs	
Immune-Mediated Nephritis and Renal Dysfunction	Administer corticosteroids at a dose of 1 to 2 mg/kg/day prednisone equivalents followed by corticosteroid taper for life-threatening (Grade 4) increased serum creatinine. Administer corticosteroids at a dose of 0.5 to 1 mg/lg/day prednisone equivalents for moderate (Grade 2) or severe (Grade 3) increased serum creatinine, if worsening or no improvement occurs, increase dose of corticosteroids to 1 to 2 mg/kg/day prednisone equivalents.	
Immune-Mediated Skin Adverse Reactions	For symptoms or signs of SJS or TEN, withhold OPDIVO and refer the patient for specialized care for assessment and treatment. If SJS or TEN is confirmed, permanently discontinue OPDIVO. For immune-mediated rash, administer corticosteroids at a dose of 1 to 2 mg/kg/day prednisone equivalents followed by a corticosteroid taper for severe (Grade 3) or life-threatening (Grade 4) rash. Withhold OPDIVO for severe	
	(Grade 3) rash and permanently discontinue OPDIVO for life-threatening (Grade 4) rash.	

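### Protocol 5.1.4.2.1 tells sites to hold nivolumab until Grade ≤1 for any immune-related event and says this matches 5.2.5, but Table 17 in 5.2.5 requires permanent discontinuation at stated severities for eight of its ten named events

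*Protocol*

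**What the plan says.** Section 5.1.4.2.1 covers management of the investigational agents when an immune-related event occurs, but its instruction also names nivolumab: "administration of the investigational study treatment and nivolumab should be interrupted until the event stabilizes to Grade ≤1". It makes no distinction by event type or grade and has no permanent-stop branch. A parenthesis then describes the rule as "consistent with guidance provided in the OPDIVO US Prescribing Information replicated in Section 5.2.5". The next sentence allows a dose reduction when the investigational agent is resumed. It does not mention resuming nivolumab.

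Section 5.2.5 consists of Table 17, a reprint of the label's management guidance. The table is specific to event and grade. Section 5.2.4, with Table 16, gives the matching dose-modification rules and says that required nivolumab changes follow the current label.

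**The concern.** The protocol states two rules for nivolumab in the same situation and asserts that they are one rule. A site that reads only 5.1.4.2.1 finds a hold that ends at Grade ≤1, with an assurance that this is what 5.2.5 says. The permanent-stop rules are missing, and the assurance gives the reader less reason to look for them.

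What is at stake is patient safety. Section 1.7.3.3 reports that single-agent nivolumab was permanently discontinued for immune-mediated pneumonitis in 1.1% of patients, for colitis in 0.7% and for hepatitis in 0.7%. After re-initiation, recurrence was about 8%, 16% and 29% respectively. These are all-grade label figures. They show that the permanent-stop branch is used and that restarting carries risk, but they do not forecast errors in this trial.

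There is also a compliance problem. Section 13.2 says the treatment regimen should not depart from the protocol. A site that correctly stops nivolumab for Grade 3 pneumonitis under Table 17 is at odds with 5.1.4.2.1 as worded.

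**Working it through.** No arithmetic figure in the plan is involved. The check sets the sentence in 5.1.4.2.1 against each row of Table 17. Named immune-mediated event types are counted. The catch-all row for other reactions and the infusion-reaction row are left out.

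| Event type | Table 17 instruction for nivolumab | Where the sentence departs from it |
|---|---|---|
| Pneumonitis | "Permanently discontinue nivolumab for severe (Grade 3) or life-threatening (Grade 4) pneumonitis" | Grade 3 and 4 |
| Hepatitis | "Withhold OPDIVO for moderate (Grade 2) and permanently discontinue OPDIVO for severe (Grade 3) or life-threatening (Grade 4) immune-mediated hepatitis" | Grade 3 and 4 |
| Adrenal insufficiency | "permanently discontinue OPDIVO for severe (Grade 3) or life-threatening (Grade 4) adrenal insufficiency" | Grade 3 and 4 |
| Encephalitis | Permanent stop once immune-mediated encephalitis is established | On diagnosis |
| Colitis | "Permanently discontinue OPDIVO for life-threatening (Grade 4) or for recurrent colitis upon restarting OPDIVO" | Grade 4 or recurrence only |
| Hypophysitis | "Permanently discontinue OPDIVO for lifethreatening (Grade 4) hypophysitis" | Grade 4 only |
| Type 1 diabetes | Permanent stop at Grade 4 hyperglycemia | Grade 4 only |
| Skin reactions | Permanent stop at Grade 4 rash or confirmed SJS/TEN | Grade 4 or confirmed SJS/TEN only |
| Hypo- or hyperthyroidism | "There are no recommended dose adjustments of OPDIVO for hypothyroidism or hyperthyroidism" | Sentence is stricter than the table |
| Nephritis | Corticosteroids only; no nivolumab dose instruction | No conflict within 5.2.5 |

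Counts:

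- Permanent stop from Grade 3: 3 event types.
- Permanent stop on diagnosis: 1.
- Permanent stop only at Grade 4, on recurrence or on confirmed SJS/TEN: 4.
- Total with a permanent stop: 3 + 1 + 4 = 8 of 10.
- No nivolumab change: 1 of 10 (thyroid).
- No nivolumab dose instruction: 1 of 10 (nephritis).

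Outside the count, the catch-all row also differs on timing. There, improvement to Grade 1 or less starts a steroid taper of at least one month, and restarting is considered only after the taper.

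The sentence does agree with part of Section 5.2. Most of the withhold rows in Table 16 carry footnote a, which resumes nivolumab at Grade 0 or 1. That footnote is in 5.2.4, however, and it applies only to the withhold rows, not to the permanent-stop rows beside them.

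**The case against.** The strongest reply is about which text governs. The paragraph sits under Investigational Agents, and its heading concerns the investigational treatment. Nivolumab has its own section, and much of the protocol points there:

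- Section 5.2.4 makes the current label govern interruption and discontinuation of nivolumab, and opens by stating that no dose modification is recommended for thyroid events.
- The Table 14 footnote points to 5.2.4 and 5.2.5, and a Table 15 footnote requires the label to be consulted.
- For suspected immune-mediated colitis and hepatitis, Sections 5.1.4.2.2 and 5.1.4.2.3 withhold all study drugs and send the site to Table 17 for immunosuppression. The stop rules sit in those same rows.
- The Study Summary, Section 3.1 and Section 5.2 say generally that nivolumab follows its label.

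The parenthesis could also be read as a pointer to 5.2.5 rather than as a separate rule.

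Most of this stands, and it lowers the practical risk. It shows which rule should prevail. It does not make the sentence correct: nivolumab is named, the hold runs to a stated grade, and agreement with 5.2.5 is asserted where there is none. Apart from the parenthesis, none of the pointers is attached to the immune-related paragraph itself.

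A reader might infer a near-total conflict by adding the thyroid row to reach 9 of 10, or Table 16's permanent stop for creatinine above 6 times ULN to reach 10 of 10. The documents do not support that reading. Four of the eight stop rows diverge only at the extreme, the thyroid difference goes in the cautious direction, and Table 16 lies outside 5.2.5, so it cannot show that the statement about 5.2.5 is false.

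**Conclusion.** Section 5.1.4.2.1 is wrong as written, and the practical risk is modest. Measured in table rows, the hold-until-Grade ≤1 rule omits a permanent stop that Table 17 requires for eight of ten named event types: from Grade 3 for three, on diagnosis for one, and only at Grade 4, on recurrence or on confirmed SJS/TEN for four. For thyroid events it asks for a hold that the label does not recommend, which is unnecessary rather than unsafe.

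A reader might go further and conclude that patients will be restarted on nivolumab after severe immune events, or that the response-rate results are affected. The documents do not support either step. The paragraph never instructs a site to resume nivolumab, a site that follows the cross-reference or the other pointers reaches the right rule, and there is no basis for an error rate.

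The conclusion rests on the ordinary reading of an interruption until Grade ≤1 as a hold with an end point, and on Table 17 as reprinted in the protocol. It should be corrected because it concerns safety and costs little.

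**What to change.** Reword the instruction along these lines: *Hold the investigational agent until the event is Grade ≤1. For nivolumab, withhold, stop permanently or continue as directed by Sections 5.2.4 and 5.2.5 (Tables 16 and 17) and the current US Prescribing Information.* Delete the parenthesis that claims consistency.

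Do not add a return-to-baseline alternative for transaminases. Table 14 offers one, but Section 5.1.4.2.3 limits that table to increases not likely to be immune-mediated. Inclusion criterion 6 admits patients with liver metastases at up to 5 times ULN, and Table 14 grades values above 3 and up to 5 times ULN as Grade 2. For such patients the alternative would allow the investigational agent to restart at Grade 2 after suspected immune hepatitis, where the present text requires Grade ≤1.

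The cost is a clarification letter or one paragraph in an amendment. No procedures, visits or patients are added.

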5.1.4.2.2 Diarrhea/Colitis

The management of diarrhea should be guided by clinical judgment and an assessment of the most likely causative etiology, with special consideration given to the potential for immune-mediated colitis. Non-specific, most often mild to moderate diarrhea has been observed with all three investigational study treatments and nivolumab. Diarrhea has been reported in approximately 55% of patients treated with glesatinib, 23% of patients treated with sitravatinib, and 46% of patients treated with mocetinostat, most often beginning within the first month of treatment. Diarrhea (any grade) is less common with nivolumab, occurring in approximately 8% (22/287) of patients treated for NSCLC with 3 mg/kg Q2W in the CheckMate 057 clinical trial (USPI OPDIVO [nivolumab]). Immune-related colitis has been reported in 2.4% (7/287) of patients treated with nivolumab for NSCLC, with median time to onset of 2.7 months (range: 4 weeks to 19 months). The presence of abdominal pain, mucus or blood in the stool or peritoneal signs should raise the index of suspicion for immune-mediated colitis, as these features are generally not observed with glesatinib, sitravatinib or mocetinostat treatment-associated diarrhea. The diarrhea observed with the investigational study treatments generally improves within several days of interrupting study medication and therefore dechallenge, with close observation may help establish the most likely causality. However, if any features of the clinical presentation, including timing of presentation, failure to improve with dechallenge, laboratory or radiologic tests suggests

the presence of immune-mediated colitis, all study medications should be withheld and treatment with immuno-suppressive therapy initiated as detailed in Table 17.

5.1.4.2.3 Increased Transaminases

The management of increases in AST and ALT should be guided by the clinical judgment of the Investigator, including an assessment of the most likely causative etiology, with special consideration given to the potential for immune-mediated hepatitis. Increased transaminases should be evaluated to determine whether confounding factors exist, such as viral infection, metastatic lesions or biliary obstruction. Tyrosine kinase inhibitors in general, and MET inhibitors in particular, have been associated with non-specific, most often mild to moderate elevation in AST and ALT. The observed effects of MET inhibitors likely reflect on-target impact on the ligand, hepatocyte growth factor (HGF). Among patients treated with glesatinib, increases in AST and ALT have been observed in approximately 18% and 12%, respectively. Mild to moderate elevations in liver transaminases have also been observed in less than 10% of patient treated with sitravatinib. The elevations observed with both glesatinib and sitravatinib generally occur within the first cycle of treatment and resolve with interruption of treatment. Nivolumab-related immune-mediated hepatitis was reported in 0.3% (1/287) of patients treated for NSCLC, with an onset of approximately 8 months following initiation of therapy.

For cases where transaminases increases are not likely to be immune-mediated, treatment management decisions should be made using Investigator discretion in consideration of clinical factors. Recommended treatment modifications are provided in Table 14. However, if any features of the clinical presentation, including timing of presentation, failure to improve with dechallenge, laboratory or radiologic tests suggests the presence of immune-mediated hepatitis, all study medications should be withheld and treatment with immuno-suppressive therapy initiated as detailed in Table 17.

Table 14: Investigational Study Treatment Modification for Increased Hepatic Transaminase¹

Toxicity	Treatment Delay	Dose Modification
Grade 1 (>ULN to 3.0 × ULN)	May be implemented based on Investigator and patient discretion	
Grade 2 (>3.0 to 5.0 × ULN)	Not required	Decrease by 1 dose level
Grade 3/4 (>5.0 × ULN)	Hold until ≤ Grade 1 or return to baseline	Decrease by at least 2 dose levels for a first dose reduction; decrease by at least 1 dose level if dose is already reduced.

1. See Sections 5.2.4 and 5.2.5 for guidelines on treatment modification for nivolumab

5.1.4.2.4 Management of Hy's Law Cases

In the event a patient develops concurrent increase in AST and/or ALT \geq 3 × ULN, bilirubin \geq 2 × ULN but without concurrent increases in alkaline phosphatase (i.e., alkaline phosphatase < 2 × ULN), that is not attributable to liver metastases or biliary obstruction, investigational study treatment should be permanently discontinued.

5.1.4.2.5 Management of Investigational Study Treatment in Event of Non-Hematological Toxicities

Per protocol, a complete review of adverse events should be conducted at each clinic visit. Symptomatic Grade 2 sitravatinib-related non-hematological adverse events occurring any time on study, particularly early in treatment (e.g., Cycle 1 Day 15 or Cycle 2 Day 1), are recommended to be managed using dose reduction to the next lower dose level, per the reduction schedule outlined in Table 9, rather than continued dosing until interruption becomes necessary.

Non-hematological toxicities \geq Grade 3 and considered to be treatment-related should be managed with investigational study treatment interruption until resolution of toxicity to \leq Grade 1 or to baseline value. If the toxicity is adequately managed by routine supportive care (such as electrolyte supplementation), treatment may be resumed at the same dose; if not, treatment may be resumed at a reduced dose (Table 15). Treatment with sitravatinib may continue without dose modification (e.g., interruption or reduction) in cases of asymptomatic amylase and/or lipase increases in the absence of other clinical evidence of pancreatitis (e.g., symptoms, electrolyte abnormalities, radiographic changes) at the investigator's discretion. Recurrence of the toxicity may be managed similarly. If treatment is interrupted for \geq 28 days, permanent discontinuation from sitravatinib should be considered.

Table 15: Investigational Study Treatment Dose Modifications – Non-Hematological Drug-Related Toxicities^{1, 2}

Toxicity	Treatment Delay	Dose Modification
Grade 1	Continue treatment unchanged	
Grade 2 Asymptomatic	May be implemented based on Investigator or patient discretion ²	
Grade 2 Symptomatic	May be implemented based on Investigator or patient discretion ² Early dose reduction to the next lower dose level is recommended over treatment interruption	
Grade 3 or 4	Hold until ≤ Grade 1 or return to baseline ²	Resume at dose one or more levels below that inducing the toxicity. Exceptions presented in footnote. ^{2,3}

Management of selected adverse events for each investigational study treatment are presented in Sections 5.1.1.4, 5.1.2.4 and 5.1.3.4.

The current OPDIVO® US Prescribing Information (USPI OPDIVO [nivolumab]) must be consulted to determine appropriate dose modifications for nivolumab.

Patients may resume at the same dose in the following cases:

- a. Grade 3 or 4 electrolyte abnormality that is not clinically complicated and resolves spontaneously or with conventional medical treatment within 72 hours;
- b. Grade 3 amylase or lipase elevation that is not associated with symptoms or other clinical manifestations (e.g., electrolyte abnormalities, radiographic changes) of pancreatitis.

5.1.4.2.6 Management of Investigational Study Treatment in Event of Hematological Toxicities

Hematological toxicities are not a frequent cause of treatment interruption or discontinuation with any of the three investigational study treatments. Observed \geq Grade 3 hematological events that are considered to be causally related to the administered investigational study treatment should be managed using treatment interruption or dose reduction at the discretion of the Investigator. If treatment is interrupted for \geq 28 days, permanent discontinuation from study treatment should be considered.

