5.1.2.3 Sitravatinib Dose Modification and Discontinuation

In the event of adverse events attributed to sitravatinib and deemed intolerable by the Investigator, treatment should be either temporarily or permanently discontinued. For patients who temporarily discontinue treatment, treatment may resume following resolution of treatment-related adverse events to Grade 1 or baseline with the administration of sitravatinib at a reduced dose level as outlined in Table 9. Once the dose has been reduced, re-escalation is generally not recommended but may be

considered on a case-by-case basis. If the administration of sitravatinib is interrupted for reasons other than toxicity, then treatment with the study drug may be resumed at the same dose.

Table 9: Sitravatinib Free Base Formulation Sequential Dose Reductions for Individual Patients

150 mg once daily (eliminated after lead-in evaluation)

120 mg once daily

80 mg once daily

60 mg once daily*

Sitravatinib Malate Direct Blend Formulation Sequential Dose Reductions for Individual Patients

60 mg once daily 40 mg once daily

Sitravatinib Malate Roller Compaction Formulation Sequential Dose Reductions for Individual Patients

100 mg once daily 80 mg once daily 60 mg once daily

40 mg once daily

A two-step dose reduction (e.g. 100 mg to 60 mg once daily) is permitted at the discretion of the investigator

In the event of sitravatinib-related AE, dose reduction with continuous treatment is preferred over repeated dose interruption. Following sitravatinib dose reduction and control of adverse event, re-challenge at a higher sitravatinib dose is permitted at the discretion of the Investigator. If treatment with sitravatinib is withheld for ≥ 28 consecutive days, then permanent discontinuation from this study drug should be considered. If one study drug is interrupted or discontinued, administration of the other study drug may continue at the discretion of the Investigator.

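### For related Grade 3 or higher non-hematological toxicities without their own rule, the text of Protocol Section 5.1.4.2.5 and its Table 15 give different restart doses

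*Protocol*

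**What the plan says.** All of this is current protocol text.

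- **Section 5.1.4.2.5, body text.** Non-hematological toxicities of Grade 3 or higher that are "considered to be treatment-related should be managed with investigational study treatment interruption until resolution of toxicity" to Grade 1 or lower, or to baseline. Then: "If the toxicity is adequately managed by routine supportive care (such as electrolyte supplementation), treatment may be resumed at the same dose". A reduced dose follows only where supportive care was not adequate, and the reference to Table 15 is attached to that second branch.
- **Table 15, Grade 3 or 4 row.** "Resume at dose one or more levels below that inducing the toxicity. Exceptions presented in footnote".
- **Table 15, same-dose footnote.** "Patients may resume at the same dose in the following cases". Two cases follow. The first is "Grade 3 or 4 electrolyte abnormality that is not clinically complicated and resolves spontaneously or with conventional medical treatment within 72 hours". The second is a Grade 3 amylase or lipase elevation without symptoms or other signs of pancreatitis.
- **Table 15, another footnote.** It points to the event-specific sections, which for sitravatinib is 5.1.2.4.
- **Section 5.1.2.3.** After an interruption for a sitravatinib adverse event that the Investigator deems intolerable, treatment may resume with "administration of sitravatinib at a reduced dose level as outlined in Table 9". Same-dose resumption is mentioned only for interruptions with a cause other than toxicity.

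**The concern.** The body text sets a general condition for returning to the same dose: routine supportive care worked. The table sets a closed list of two cases. The first is much wider than the second, and neither passage says which prevails.

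Two sites that both believe they are following the protocol can restart similar patients at different doses. The first consequence is safety on re-exposure. The second is interpretation. The SAP plans to report patients with at least one dose reduction (Section 11.1.7.1), TEAEs leading to dose reduction or interruption (Section 11.1.7.2), and sitravatinib relative dose intensity, with the starting daily dose in the denominator (Section 8.3.4). Each would partly reflect which passage a site followed rather than how well the regimen was tolerated.

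**Working it through.** The plan gives no figure to reproduce here. The check sets the rules side by side and applies them to test cases.

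| Place | Applies to | Same dose | Lower dose |
|---|---|---|---|
| 5.1.4.2.5 text | Related non-hematological, Grade 3 or higher, resolved | Permitted if routine supportive care was adequate | If it was not |
| Table 15, Grade 3 or 4 row and same-dose footnote | Drug-related non-hematological, Grade 3 or 4, resolved | Two listed cases | All others |
| 5.1.2.3 | Sitravatinib event deemed intolerable, drug interrupted | Mentioned only for non-toxicity interruptions | After toxicity |
| 5.1.2.4.1 | Grade 3 hypertension with clinically significant increase | Same or lower, Investigator's discretion | Same or lower, Investigator's discretion |
| 5.1.2.4.3 | Diarrhea | No restart dose stated | No restart dose stated |

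**Test cases**

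1. *Related Grade 3 vomiting, controlled with anti-emetics, resolved to Grade 1.* Text: same dose permitted. Table 15: at least one level lower, because vomiting is not in the footnote. Section 5.1.2.4 has no entry for vomiting or nausea. The rules conflict.
2. *Uncomplicated Grade 3 electrolyte abnormality corrected by supplementation, but only after more than 72 hours.* Text: same dose permitted, since this is its own example. Table 15: lower, because the 72-hour limit was missed. The rules conflict.
3. *The same abnormality corrected within 72 hours.* Both allow the same dose. No conflict.
4. *Any Grade 3 event that supportive care did not control adequately.* Both lead to a lower dose, apart from the footnote cases. No conflict for events outside the footnote.
5. *Grade 3 diarrhea controlled with loperamide.* Table 15's footnote leads to 5.1.2.4.3, which allows a restart once diarrhea is controlled but names no dose. The answer is unclear.
6. *Grade 3 hypertension of the kind in 5.1.2.4.1.* It has its own rule and lies outside the conflict.

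**Size for one patient.** On the free-base ladder in Table 9, the step below 120 mg is 80 mg: (120 − 80)/120 = 33% lower. Under SAP Section 8.3.4, each day after restart contributes 120/120 = 100% of planned dose in one case and 80/120 = 67% in the other.

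**How many patients.** Table 5 (monotherapy Study 516-001, N = 153) gives these Grade 3 or higher related events:

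- nausea: 5/153 = 3.3%
- vomiting: 4/153 = 2.6%
- diarrhea: 16/153 = 10.5%

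Nausea or vomiting together is 5 patients if they overlap as far as possible and 5 + 4 = 9 if they do not, that is 3.3% to 5.9%. Each count is an upper limit for that event in that study, because the rules diverge only if the event resolved, supportive care was adequate and the drug was restarted.

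**The case against.** The best defense has four parts.

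*The body text is permissive.* It says treatment may resume at the same dose, so a site that reduces under Table 15 breaches neither passage. That is correct, and it narrows the point: the conflict arises only when a site uses the permission outside the two footnote cases and the event-specific rules. It does not remove the conflict, because the table row is directive and does not list investigator discretion among its exceptions.

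*The text refers to Table 15.* It does, but only on the reduced-dose branch. The same-dose branch stands before it with its own, broader condition.

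*Other sections soften the picture.* A reader might infer that Section 5.1.2.3 requires a reduced dose after every Grade 3 or 4 event. It does not: it covers events deemed intolerable, whatever the grade, says treatment may resume, and permits re-challenge at a higher dose at the Investigator's discretion once the event is controlled. Nor are the two footnote cases the only route to the same dose, given the hypertension rule. Hematological toxicities fall outside the point, since 5.1.4.2.6 leaves them to the Investigator.

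*The size is easily overstated.* Scaling diarrhea to the 125-patient cohort gives 16/153 × 125 = 13, and a reader might take that as the number affected. The documents do not support it. It counts every Grade 3 or higher case, including those where supportive care failed, and diarrhea is unclear rather than plainly contradictory. The source is monotherapy in a study that escalated from 10 to 200 mg. One might also infer an effect on planned recurrent-toxicity summaries. None is planned: SAP Section 11.1.7.2 counts a patient once per SOC or preferred term.

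**Conclusion.** The inconsistency is real and confined to treatment-related, non-hematological toxicities of Grade 3 or higher. It is plain for events that routine supportive care controls, that lie outside the two footnote cases and that have no rule of their own; nausea and vomiting are the clear examples. Diarrhea is unresolved because its section gives no restart dose. Section 5.1.2.3 adds to the inconsistency, but the conclusion does not depend on it.

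For a patient still at 120 mg on the free-base capsule, the difference is one third of the dose or more. A patient already reduced, for example under the early-reduction advice for symptomatic Grade 2 events, would face a different step. How many patients would meet the conflict cannot be estimated reliably. The Table 5 counts are upper limits for that study's patients and need not carry over to 120 mg with nivolumab. Table 6, the combination experience, would be the better source, but its rows were not available for this check.

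Nothing here bears on the type 1 error or power of the ORR analysis. The stakes are consistent re-exposure and the meaning of the dose-reduction and relative-dose-intensity summaries. The passages should be reconciled; this review takes no position on which rule is right.

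**What to change.** Reconcile the 5.1.4.2.5 body text, the Table 15 Grade 3 or 4 row with its footnotes, and Section 5.1.2.3, so that a single statement governs when same-dose resumption is allowed. The other passages and the event-specific sections in 5.1.2.4 should refer to it, including 5.1.2.4.3, which now names no restart dose. The sponsor's medical team decides the content.

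The cost is wording in a few sections and one table, issued as an administrative letter or amendment with IRB/EC submission under Section 13.1. It needs no new procedures, data or sample-size change.
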